## *Data Analysis Strategy.*

**Overview of Data Analyses.** Our study team specializes in statistical analysis and measurement models related to those described in this proposal. [name] and our team biostatistician (co-I [name]) will coordinate the data analytic aspects of the project, and carry out the proposed mixed effect linear models (MLMs). A secure de-identified database will be maintained by the PI and project coordinator (see Budget Justification). A CONSORT flowchart will be generated in Year 1 that tracks participants through the study. Descriptive statistics will be used to characterize the sample, and chi- square and one-way ANOVAs will be used to evaluate success of randomization on primary variables of interest. In addition to the MLMs presented below, as a sensitivity analysis we will also consider MLMs that adjust for baseline variables of interest. To help explain study attrition, chi-square and independent-sample t-tests will compare dropouts to non-dropouts. We are defining successful treatment completion as having completed 11 out of the 14 available lessons. While our primary analyses follow intention-to-treat principles, we will also assess how sensitive results are to excluding subjects who do not successfully complete their respective treatment.

Treatment groups will be dummy coded with CC (coping control) used as the reference group. We will test for treatment condition effects on the stress and symptom outcome measures using MLMs as we did in our publications in the R21 feasibility trial. MLMs provide an optimal analytic strategy because they model all available data (following intent-to-treat principles in RCTs) and allow us to flexibly evaluate the nested nature of this data structure. Specifically, we will create (for EMA) 3-level MLMs (levels: individual participants; day; within-day time) using restricted maximum likelihood estimation. The 3-level EMA MLMs testing each aim will compare the 3 treatment intervention groups on each dependent variable (e.g., daily stress) from the pre, post, and follow-up training measurement occasion. The 3-level models will include a random intercept for day nested within participant. Measurement occasion (pre, post intervention, follow-up), group condition, day-specific factors (e.g., day-of-week or weekday versus weekend), and within-day time will be modeled as fixed effects. All models will be fit with compound symmetric variance-covariance data structure but other structures (e.g., autoregressive covariance structure, ARH(1), spectral power) will be evaluated using Akaike's Information Criterion (AIC). We have specified this initial approach for modeling random and fixed effects, but we will evaluate whether this approach best fits the data using likelihood ratio tests and AIC. In testing each aim, each measurement occasion  $\times$  treatment interaction will be evaluated with a decision rule that a significant effect is observed when the measurement occasion  $\times$  treatment interaction statistic and corresponding p-value is less than .05 (two-tailed). When a significant interaction is observed, follow-up planned contrasts in each MLM will compare specific groups at post-training. To help with benchmarking we will provide effect size statistics corresponding to the magnitude of change over time, and between groups at each post-treatment time point. One strength of our approach here is that it extends an established MLM data analytic pipeline we used in our three-arm EMA R21 trial publications with success, along with MLM mediation analyses in other MBSR RCT publications.

**Testing our Hypotheses.** We are specifying a priori predictions about the effects of MA-MBSR intervention, relative to MO-MBSR and CC. Thus no statistical corrections for multiple comparisons will be made for our primary study hypotheses or specified pair-wise comparisons. When additional exploratory analyses are conducted, a Holm's correction will be made for multiple comparisons. We have previously published our MLM approach evaluating MA-MBSR effects relative to these two control groups (see Chin et al., 2019 or Lindsay et al., 2018 publications)—so here we highlight our equations and approach. In previous work we have focused on stress, so below we apply this approach to evaluating hypothesis #2, specifying that MA-MBSR will reduce symptoms relative to MO-MBSR and CC. This hypothesis will be tested separately for clinician assessed, physician assessed or patient self-reported symptoms (using the IBS-SS). The general form of the model to be tested, exclusive of covariates, is as follows, in mixed model

notation:

IBS symptomsit =  $\gamma_{00} + \gamma_{01} \cdot (\text{txgroup}_i) + \gamma_{10} \cdot (\text{time}_{it}) + \gamma_{11} \cdot (\text{txgroup}_i) \cdot (\text{time}_{it}) + u_{0i} + e_{it}$  where IBS symptomsit is the composite symptoms score for individual  $i$  at time-point  $t$ , timeit is the measurement occasion (pre, post intervention, or follow-up) assessment time of year, txgroupi is the treatment group a participant is assigned to. In multilevel notation:

$$\begin{aligned} \text{Level 1: } & \text{Symptoms}_{it} = \beta_{0i} + \beta_{1i} \cdot (\text{time}_{it}) + e_{it} \\ \text{Level 2: } & \beta_{0i} = \gamma_{00} + \gamma_{01} \cdot (\text{txgroup}_i) + u_{0i} \\ & \beta_{1i} = \gamma_{10} + \gamma_{11} \cdot (\text{txgroup}_i) \end{aligned}$$

The primary test of hypothesis is the F-test of the null hypothesis  $H_0: \gamma_{11} = 0$ . Note that this general model will be used, with different outcomes (e.g., stress) and for subsequent aims below but will not be repeated.

For hypothesis #3, we will use EMA-sampled IBS symptom severity to test whether EMA-sampled stress reduction will statistically mediate symptom improvements. We will test for concurrent relations between EMA-sampled stress and IBS symptom severity (within the same moment) and also test lagged relations (stress at time  $t$  predicting IBS symptom severity at time  $t+1$ ). To conduct this mediation analysis, we will compare two MLMs that use IBS symptom severity as the outcome and group condition as a fixed effect: one MLM will include stress as an additional fixed effect, and another will not. If the fixed effect for group condition is statistically significant in the latter but not the former, stress reduction will be declared to act as a mediator for symptom improvements.

For hypothesis testing, we will first run unadjusted models without covariates, as described above. Then, as a sensitivity analysis, we will run adjusted models that incorporate baseline characteristics related to sociodemographic covariates (sex, gender, age, race), clinical covariates (IBS subtype, baseline IBS symptom severity, baseline perceived stress), and other time-related covariates such as day-of-week when appropriate (e.g., for analyses involving EMA samples where we observe repeated measures across and within days).

**Attrition and Missing Data.** We expect minimal participant attrition (<15%) during the study period across conditions. Dropouts are not expected to be a function of the missing outcome data given the observed. Our unadjusted analyses assume data are missing completely at random, while our adjusted analyses loosen this assumption to allow for data to be missing at random. We will also assess the sensitivity of our results to violations of the missing-at-random assumption (e.g., via pattern-mixture models). Additionally, we will evaluate whether adherence to the program and EMA vary across groups. To evaluate attrition, we will compare study dropouts to study completers based on observed participant characteristics.

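### The planned exclusion of treatment non-completers selects on behaviour after randomisation, so it cannot serve as a robustness check of the intention-to-treat result

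*SAP*

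**What the plan says.** The Overview of Data Analyses sets the completion rule: "We are defining successful treatment completion as having completed 11 out of the 14 available lessons". The next sentence keeps randomised groups for the main analysis ("While our primary analyses follow intention-to-treat principles") and then adds the secondary one: "we will also assess how sensitive results are to excluding subjects who do not successfully complete their respective treatment". The threshold is the same number in every arm, but each person is judged on the programme to which they were assigned.

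The models "will compare the 3 treatment intervention groups on each dependent variable", and the effect of interest is the occasion-by-treatment interaction.

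Three other planned steps come near this point:
- Under Attrition and Missing Data, "we will evaluate whether adherence to the program and EMA vary across groups".
- Under Testing our Hypotheses, adjusted models are a separate sensitivity analysis. Their covariates include "clinical covariates (IBS subtype, baseline IBS symptom severity, baseline perceived stress"), along with sociodemographic variables.
- Also under Attrition and Missing Data, pattern-mixture models are offered for departures from missing at random.

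None of the three is tied to the completer subset. The SAP names no estimand for the exclusion analysis and gives no caution on how to read it.

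**The concern.** Lesson completion happens after randomisation and may depend on how a person is doing in the programme received. Dropping non-completers from MA-MBSR, MO-MBSR and CC therefore leaves three self-selected groups, each selected by finishing a different programme. Those groups are no longer comparable by design.

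The SAP presents the exclusion as a test of how sensitive its results are. It cannot answer that question. It changes the population and the question together, so neither agreement nor disagreement with the intention-to-treat estimate separates an effect of completing lessons from an effect of who completes. What is at stake is the reading of a pre-specified secondary result: selection alone could create a completer difference or hide a real one.

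The concern is narrower than prognosis in general. A stable difference in symptom level between completer groups falls into the group main effect. Only selection related to symptom change reaches the interaction that the plan tests.

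**Working it through.** **Inputs from the SAP.** Three arms; completion at 11/14 = 78.6% of lessons; significance level 0.05 two-sided ("corresponding p-value is less than .05 (two-tailed"). The one loss figure, "We expect minimal participant attrition (<15%) during the study period across conditions", concerns study dropout. It does not bound the share who finish fewer than 11 lessons. The SAP gives no sample size, completion rate or effect size, so there is no planned figure to reproduce.

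**Assumptions.** Completion share p in each arm; correlation rho between a latent tendency to complete and symptom change (SD 1); true treatment effect zero; for error rates, 100 participants per arm. None of these comes from the SAP.

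**Bias.** A person completes when the latent tendency exceeds a cutoff c = z(1 − p). The mean change among completers is shifted by rho × λ(p), with λ(p) = φ(c)/p. The bias between two arms is rho_A × λ(p_A) − rho_B × λ(p_B).

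λ(0.70) = 0.497, λ(0.80) = 0.350, λ(0.90) = 0.195.

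- 70% versus 90%, same rho in both arms: 0.497 − 0.195 = 0.302. Size of bias: 0.2 × 0.302 = 0.06 SD; 0.3 × 0.302 = 0.09 SD; 0.5 × 0.302 = 0.15 SD.
- 80% in both arms, same rho: rho × (0.350 − 0.350) = 0.
- 80% in both arms, opposite-sign rho (faster improvers finish in one arm, slower improvers in the other): 0.2 × 0.700 = 0.14 SD; 0.3 × 0.700 = 0.21 SD.

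The last two lines show that equal completion rates neither cause nor exclude bias. What matters is whether selection is the same in each arm.

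**False-positive rate of a two-arm completer comparison.** The variance within completers is v = 1 − rho² × λ × (λ − c). The standard error is SE = √[v_A/(n p_A) + v_B/(n p_B)]. The rejection probability is Φ(−1.96 − bias/SE) + Φ(−1.96 + bias/SE). With n = 100 per arm:

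| Completion | rho | Size of bias (SD) | Rejection rate |
|---|---|---|---|
| 85% / 85% | 0.3 / 0.3 | 0 | 5.0% |
| 85% / 70% | 0.3 / 0.3 | 0.067 | 7.1% |
| 85% / 85% | 0.3 / 0 | 0.082 | 8.4% |
| 90% / 60% | 0.3 / 0.3 | 0.135 | 13.1% |
| 85% / 85% | 0.3 / −0.3 | 0.165 | 19.4% |
| 90% / 60% | 0.5 / 0.5 | 0.224 | 29.9% |

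A simulation of the last row (20,000 runs) gave a bias of 0.22 SD and a rejection rate of 29.4%. These rates apply to a simple two-group comparison of change scores, not to the full three-arm mixed model.

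**The case against.** The best defence is that the exclusion is secondary. Intention-to-treat is primary, the exclusion has no decision rule of its own, and completer analyses beside intention-to-treat are routine. This stands: the primary conclusion and its error rate are not touched.

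A second defence is that the SAP already plans to compare adherence across groups, which would reveal a gap such as 70% versus 90%, and already plans baseline adjustment. This stands in part. The adherence comparison covers rates, not who finishes, and the SAP applies neither step to the completer subset.

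A third is that every magnitude is assumed. This is true. The more ordinary case, selection in the same direction in both arms, gives small figures, and identical selection gives none. The opposite-direction figures of 0.14 to 0.21 SD are extreme illustrations, not expectations.

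A reader might also infer that the team would report a larger completer effect as support for the programme and a smaller one as fragility. The SAP does not say so; it says only that sensitivity to the exclusion will be assessed.

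Finally, weighting on baseline variables is not a full cure. If people stop because of how they respond to early lessons, baseline weights remove only the part that baseline variables predict. This stands and limits what the fix may claim.

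**Conclusion.** The point holds as a modest improvement to a secondary analysis. Excluding non-completers within each arm compares groups formed after randomisation. If completion is related to symptom change, and that relation or the completion rate differs by arm, the contrast is biased in either direction. Illustratively the bias is 0.06 to 0.09 SD for 70% versus 90% completion at rho 0.2 to 0.3, and zero if selection is the same in all arms. Completion rates, rho and numbers per arm are all assumptions.

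It would be wrong to conclude that the trial's main finding is at risk, that any prognostic difference between completers biases the tested interaction, or that bias is certain. The documents support only that the analysis, as described, cannot do the job of a robustness check, and that no other planned step repairs it.

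**What to change.** Amend the SAP as follows:

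1. Label the plain exclusion analysis descriptive, and say that it is not a robustness check of the intention-to-treat result.
2. Present it with the number and share completing at least 11 of 14 lessons in each arm, using the adherence comparison already planned.
3. Add a completer analysis weighted by the inverse of the estimated probability of completion. Model completion on baseline symptom severity, perceived stress, IBS subtype, age and sex, all already listed as covariates. Fit the model by arm, or as one pooled model with arm terms if non-completers are few, since separate models could then be unstable. Fit the same mixed model to the weighted completers with robust standard errors.
4. State that the weights remove only selection explained by the measured baseline variables, so selection on response during the programme remains, and that the intervals will be wider.

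The cost is a few sentences of SAP text and the logistic modelling. No new data are needed. Fixing the method now also avoids choosing it after the results are seen.

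### The EMA mixed model names no participant-by-occasion random effect, so its occasion-by-treatment test is too liberal if participants differ in their own change

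*SAP*

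**What the plan says.** All of this is in the SAP, Data Analysis Strategy.

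- **Levels.** The EMA outcomes get "3-level MLMs (levels: individual participants; day; within-day time) using restricted maximum likelihood estimation". Occasion is not a level.
- **Random part.** "The 3-level models will include a random intercept for day nested within participant".
- **Fixed part.** The list begins "Measurement occasion (pre, post intervention, follow-up), group condition, day-specific factors" and goes on to within-day time. Occasion appears only here.
- **Covariance.** "All models will be fit with compound symmetric variance-covariance data structure but other structures" will be compared by AIC. The examples given are autoregressive, ARH(1) and spectral power. The factor to which compound symmetry applies is not stated.
- **Model checking.** The specification is called an initial approach, and "we will evaluate whether this approach best fits the data using likelihood ratio tests and AIC".
- **Decision rule.** For each aim the occasion-by-treatment interaction is tested at a two-sided 0.05. A significant result opens the planned group contrasts.
- **General model (Testing our Hypotheses).** It has a participant intercept u_0i and a residual e_it, and no random term on the time slope. It is to serve other outcomes too: "Note that this general model will be used, with different outcomes (e.g., stress) and for subsequent aims below but will not be repeated".

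**The concern.** The interaction asks whether arms differ in how much participants change between occasions. The relevant noise is how much participants within an arm differ in that change. All EMA days of one person at one occasion share that person's level at that occasion, so extra days do not average this variation away.

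A model with participant and day intercepts only has nowhere to put it. It spreads the variation over the many day-level degrees of freedom, and the standard error of the interaction comes out too small. With one score per person per occasion, as for the IBS-SS, e_it absorbs the variation and the general model has the right error term. The problem is confined to the EMA outcomes, such as daily stress.

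At stake are the 0.05 level for every EMA aim, the contrasts that a significant interaction opens, and the confidence intervals reported with them. The SAP makes no multiplicity correction for the primary hypotheses, so nothing downstream offsets a liberal test.

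**Working it through.** The SAP states no power, sample size or variance, so the only figure to check is the nominal 0.05.

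**Inputs from the SAP:** 3 arms and 3 occasions, so the interaction has (3−1)×(3−1) = 4 df; two-sided 0.05; random effects for participant and for day within participant. The participant intercept is read from the named level and from u_0i in the general model.

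**Assumptions (not in the SAP):** balanced data; 60 per arm (N = 180); total variance 1; participant share 0.40; day share sv2 = 0.10 or 0.15; participant-by-occasion share sw2 = 0, 0.02, 0.05 or 0.10; residual se2 = the remainder; K = 1 or 5 prompts a day; D = 3 or 7 days per occasion.

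**Formulas**

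- Correct error: E[MS participant×occasion] = se2 + K·sv2 + K·D·sw2, on 2(N−3) df.
- Day-level error: E[MS day] = se2 + K·sv2, on 3N(D−1) df.
- The stated model pools the two, weighted by their df.
- R = correct error / pooled error. Type I error ≈ P(chi-square on 4 df > 9.488/R). Correct intervals are √R times as wide.

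**Mildest cell (K = 1, D = 3, sw2 = 0.02, sv2 = 0.10, se2 = 0.48)**

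- Correct error 0.58 + 0.06 = 0.64; day error 0.58; df 354 and 1,080.
- Pooled (354×0.64 + 1,080×0.58)/1,434 = 0.595; R = 1.076.
- 9.488/1.076 = 8.82, so type I error is 6.6%; √R = 1.04.

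**A stronger cell (K = 5, D = 7, sw2 = 0.05, sv2 = 0.10, se2 = 0.45)**

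- Correct error 0.95 + 1.75 = 2.70; day error 0.95; df 354 and 3,240.
- Pooled (354×2.70 + 3,240×0.95)/3,594 = 1.122; R = 2.406.
- 9.488/2.406 = 3.94, so type I error is 41.4%; √R = 1.55.

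**All cells** (exact F-test, 400,000 draws each), type I error in %:

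| Prompts/day, days | Day share | sw2 = 0 | 0.02 | 0.05 | 0.10 |
|---|---|---|---|---|---|
| 1, 3 | 0.10 | 5.0 | 6.6 | 9.3 | 14.6 |
| 1, 7 | 0.10 | 5.0 | 9.9 | 18.7 | 34.2 |
| 5, 3 | 0.10 | 5.0 | 9.8 | 17.4 | 28.4 |
| 5, 7 | 0.10 | 5.0 | 20.5 | 41.4 | 61.1 |
| 5, 3 | 0.15 | 5.0 | 9.0 | 15.4 | 25.1 |
| 5, 7 | 0.15 | 5.0 | 17.9 | 36.3 | 56.0 |

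With one rating a day, day and residual variance cannot be separated, so the day share does not matter.

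**Interval width.** For 1 rating and 3 days, R runs from 1.076 to 1.394, so correct intervals are 4 to 18% wider. For 5 prompts and 7 days, R runs from 1.505 (day share 0.15, sw2 = 0.02) to 3.535 (day share 0.10, sw2 = 0.10), so they are 23 to 88% wider.

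**Checks**

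- At day share 0.10, results for 30, 60 and 100 per arm agree within 1 point.
- Adding sw2 on top of the total, in place of carving it out of the residual, lowers the figures by at most about 4 points.
- Direct simulation (4,000 trials per cell, sw2 = 0.05) gave 8.9% (1 rating, 3 days), 17.5% (5, 3) and 42.4% (5, 7). The general model applied to participant-by-occasion means held 4.6 to 5.4%.
- Other inputs (30 or 80 per arm; variances 0.4 participant, 0.1 day, 0.5 residual) gave about 16% and 25% for 4 prompts over 3 days at participant-by-occasion variances 0.05 and 0.10, and about 40% and 58% for 5 prompts over 7 days. With the term in the model, every scenario lay between 4.3 and 5.6%.

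**The case against.** The strongest reply is that the figures describe a starting model. The SAP commits the team to checking the random part by likelihood ratio and AIC. Had AIC been offered this term (60 per arm, day share 0.10), it would have chosen it in 39% of trials in the mildest cell and in at least 90% in every other non-zero cell. Type I error after selection would be 5.0 to 5.6%. That stands, and it means the upper figures are not a forecast of the trial's error rate. But the SAP names no such candidate and gives no rule for adopting one.

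Second, the power-type correlation that the SAP lists would absorb part of the missing variance, because it ties together days within an occasion. A large-sample calculation with an assumed 60-day gap between occasions gives 5.5 to 7.3% (1 rating, 3 days), 8.3 to 21.9% (1, 7), 6.0 to 6.5% (5, 3) and 13.8 to 20.4% (5, 7). This reduces the inflation, but with 7 days it stays material.

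Third, compound symmetry placed on occasion within participant would supply the term. That reading is possible, since a day intercept already makes prompts within a day exchangeable. The factor is not stated, so the text does not settle it.

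Fourth, the full random part may be in the team's earlier publications, to which the SAP refers. Those are not at hand, and the SAP's own statement of the model should not depend on them.

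**Conclusion.** The concern holds and should be fixed. The EMA model as written has no participant-by-occasion random effect, and its interaction test exceeds 0.05 whenever participants differ in their own change. That direction holds under the ordinary reading with a participant intercept; the size depends on inputs the SAP does not give. With a participant-by-occasion share of 2 to 10%, it runs from 6.6 to 14.6% in the lightest EMA schedule considered and from 17.9 to 61.1% in the heaviest. These rates apply if the model is run as stated and the term is not added at the checking stage. At zero share the test is correct. Outcomes with one value per person per occasion are not affected.

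**What to change.** Write the EMA random part as three terms: a participant intercept, a participant-by-measurement-occasion effect, and day nested within participant-by-occasion. Keep them in the model whatever AIC or the likelihood-ratio tests suggest, and use those criteria only for further refinements. Retaining the term changes the error rate little compared with letting AIC choose it (5.0% against 5.0 to 5.6%), but it fixes the error term in advance. State the factor to which the compound-symmetric structure applies. As a check, repeat the interaction test on participant-by-occasion EMA means with the general model from Testing our Hypotheses.

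The cost is a sentence or two in the SAP, one extra variance component, and somewhat wider intervals for the EMA interaction. Design and data collection do not change.

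### Three-occasion models: the primary interaction test is valid but uses baseline only through change scores; with an adequate covariance structure, a common-baseline model is at least as precise at almost no cost

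*SAP*

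**What the plan says.** In the SAP under Testing our Hypotheses, the model for IBS symptoms has a treatment main effect (γ01), a time effect, their interaction (γ11) and a participant random intercept, with no covariates. The time variable "is the measurement occasion (pre, post intervention, or follow-up", so the pre score is an outcome row. "The primary test of hypothesis is the F-test of the null hypothesis" that γ11 is zero. The model is reused: "Note that this general model will be used, with different outcomes (e.g., stress" is given as an example.

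The preceding section (Data Analysis Strategy, paragraph on MLMs) makes a significant interaction at two-sided 0.05 the condition for going further. Then "follow-up planned contrasts in each MLM will compare specific groups at post-training". It does not say whether these contrasts compare raw post scores or changes from pre. The default covariance is fixed there too: "All models will be fit with compound symmetric variance-covariance data structure", with alternatives to be compared by AIC.

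Baseline adjustment comes second. For hypothesis testing, "we will first run unadjusted models without covariates, as described above". The Overview of Data Analyses says that "as a sensitivity analysis we will also consider MLMs that adjust for baseline variables of interest". The later list of adjusted models includes "clinical covariates (IBS subtype, baseline IBS symptom severity, baseline perceived stress", without saying whether the pre score then stays as an outcome row.

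**The concern.** If pre is measured before randomisation, the arms have the same expected baseline mean. The stated model does not use this: γ01 lets baseline means differ freely by arm. Chance baseline differences are then subtracted in full, with weight 1, instead of in proportion to how well baseline predicts the later score. The result is unbiased but noisier than it need be, most of all when r is low.

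The interaction test is both the primary test and the condition for the pairwise contrasts, so lost power there also blocks the comparisons of interest. Because the model is reused for other outcomes, the loss recurs wherever three occasions are analysed this way.

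**Working it through.** **Inputs.** From the SAP: three arms, three occasions, free γ01, no covariates, compound symmetry by default, two-sided 0.05. It states no sample size, SD, effect size, power or r, so there is no figure to reproduce. Assumed: r = 0.3, 0.5, 0.8; equal arms; equal SDs; only MA-MBSR differs; occasion categorical; complete data unless stated.

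**Step 1: variance of one contrast, per arm, in units of σ².**
- Stated model, interaction (difference in change): 2(1-r) = 1.40, 1.00, 0.40.
- Raw post difference: 1.
- Common baseline: 1-r² = 0.91, 0.75, 0.36.

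Against the change reading the difference is 2(1-r) - (1-r²) = (1-r)², and the ratio is (1+r)/2 = 0.65, 0.75, 0.90. That is a variance cut of 35%, 25% and 10%. Against the raw reading the difference is r², a cut of 9%, 25% and 64%. Neither difference is ever negative.

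**Step 2: the joint 4-df test.** With I the identity matrix and J the matrix of ones, the covariance of the (post, follow-up) effects is proportional to (1-r)(I + J) in the stated model and (1-r)(I + rJ) with a common baseline. The noncentrality ratio, stated over common baseline, is:
- effect at post only: 2(1+2r)/[3(1+r)] = 0.821, 0.889, 0.963;
- effect equal at post and follow-up: (1+2r)/3 = 0.533, 0.667, 0.867;
- equal and opposite effects: 1, no gain.

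**Step 3: power.** Set the common-baseline test at 80% power, scale its noncentrality by these ratios, and use the noncentral chi-square on 4 df:

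| Assumed r | Stated test, post only | Stated test, sustained |
|---|---|---|
| 0.3 | 70.6% | 49.6% |
| 0.5 | 74.5% | 60.2% |
| 0.8 | 78.3% | 73.3% |

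**Step 4: robustness.**
- With 15% of participants having pre only, at r = 0.5 the stated test has 75.1% and 62.8%.
- If γ11 is read as one linear slope (time coded 0, 1, 2; 2 df), the stated test has 57.0%, 65.6% and 75.2%.
- Simulation with 60 per arm (assumed) and unstructured covariance in the common-baseline model gives gains of 8, 4 and 1 points (post only) and 30, 19 and 5 points (sustained). Null rejection is 4.5-5.1% for the stated test and 4.9-5.2% for the alternative.

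**Step 5: the adjusted sensitivity models, both readings.**
- *Pre dropped as an outcome row.* The post contrast is ordinary baseline adjustment and reaches 1-r², but only as a sensitivity result.
- *Pre kept as an outcome row.* With complete data and compound symmetry, adding the baseline score leaves the interaction unchanged. On one simulated dataset (r = 0.5) the estimate was 0.2233 and the standard error 0.1428 both with and without it; the common-baseline standard error was 0.1224.

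In the second reading a raw post contrast has a standard error that is too small. The fitted baseline slope is b = (1+2r)/3. The true factor is 1 - 2br + b² = 0.964, 0.778, 0.364. The model reports the average over the three occasions, [(1-b)² + 2(1 - 2br + b²)]/3 = 0.716, 0.556, 0.249. At r = 0.5 the critical value shrinks to 1.96 × √(0.556/0.778) = 1.66, so null rejection is 9.8%; at 0.3 and 0.8 it is 9.1% and 10.5%. These rates ignore the rule that contrasts follow only a significant interaction. With that rule and no arm differing, simulated rejection is about 2% (1.8%, 1.9%, 2.1%).

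**The case against.** The strongest reply is that nothing here is an error. An arm-by-occasion model with a free arm effect is conventional, unbiased under randomisation, holds its level, and follows the team's published approach. That stands: the point is efficiency, and a reader should not infer that the primary test is biased or invalid.

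Three further inferences are tempting and not supported.

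- *A common baseline always wins.* It does so when the covariance is adequately modelled; the difference is then (SD_pre - r·SD_post)², never negative. If compound symmetry is forced while the SD grows after baseline, it can lose. The variance ratio is 1.11 for an SD ratio (post to pre) of 1.2 with r = 0.9, and 1.13 for 1.5 with r = 0.7. With the correct covariance the same cases give 0.98 and 1.00 (0.977 and 0.998).
- *The sensitivity analyses can never recover the gain.* The SAP does not say whether pre stays as an outcome row, and if it is dropped the post contrast does recover it.
- *The trial will have 10% false positives.* That figure needs pre kept as an outcome row, a raw contrast and no preceding interaction test, and it concerns a sensitivity model only. The excess matters mainly when the interaction is significant because another arm differs.

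It is also fair that r is unknown, that the largest gains need low r and a sustained effect, and that the constraint requires pre to precede randomisation, which the SAP does not state and the protocol may. These limit the size and set a condition; they do not remove the point.

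**Conclusion.** The point holds as an efficiency improvement to the three-occasion, non-EMA models. The stated primary test is valid but leaves unused some precision that the planned data already contain. On the assumptions above, the stated test falls short of a common-baseline test at 80% power by about 9, 5 and 2 points for an effect at post only, and by about 30, 20 and 7 points for a sustained effect, at r = 0.3, 0.5 and 0.8. The shortfall is zero for equal and opposite effects and shrinks as r approaches 1. The actual loss in this trial cannot be stated, because the SAP gives neither r nor a sample size. Nothing is claimed for the three-level EMA models, where the comparison was not checked.

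A secondary point is conditional. The adjusted models should not carry the outcome's baseline value as a covariate beside its own pre row, because a raw post contrast would then look more certain than it is.

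**What to change.** Provided pre is measured before randomisation (confirm this first), make the primary three-occasion analysis a constrained longitudinal model:

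- categorical occasion, with one common baseline mean for all arms (no treatment effect at pre);
- treatment-by-post and treatment-by-follow-up terms, tested jointly (4 df) as the primary test;
- unstructured covariance in place of default compound symmetry;
- post-training contrasts taken from the same model, which makes them baseline-adjusted and settles whether they are raw or change comparisons.

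Keep the stated model as a sensitivity analysis. In the adjusted models, state whether pre remains an outcome row; if it does, leave the baseline value of that outcome out of the covariates.

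The cost is SAP wording before analysis, with no extra data or visits. Unstructured covariance for three occasions has six parameters against two for compound symmetry, so four more are estimated. Participants with only a pre score stay in the model.
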